## 7. Research Plan:

The study is a randomized, open-label, comparative effectiveness clinical trial in 180 total patients with GERD or dyspepsia symptoms who will be randomized to either conventional or genotype-supported treatment of GERD and dyspepsia. A total of 120 patients will be enrolled in the UF Health Gastroenterology Clinics in Gainesville, and 60 will be enrolled in a parallel study (under separate IRB protocol) at Nemours Children's Hospital Gastroenterology Clinics in Orlando, FL. Each site will be responsible for overseeing patient care and research at their respective facility. All participants will have symptoms of GERD or related diseases and be candidates for PPI therapy or on PPI therapy with continued symptoms.

We will enroll a total of 180 patients between the UF Health and Nemours sites, which should allow for sufficient power to detect our efficacy endpoint (see power calculation below). We will also collect data from the health records for up to 24 months after enrollment on upper respiratory infection (cold), sore throat, strep throat, bronchitis, pneumonia, ear infection, acute sinusitis (sinus infection), bone fractures, renal function, and gastrointestinal infections for preliminary assessment of the effects of *CYP2C19*-supported PPI dosing on adverse effects. This exploratory arm will provide data to inform power calculations for a larger study focused on preventing PPI-associated adverse events through genotype-supported dosing.

**Inclusion Criteria.** A total of 120 patients with GERD or related symptoms will be enrolled at UF Health. An additional 60 patients will be enrolled at Nemours Children's Hospital Gastroenterology Clinics under a separate IRB protocol. For this protocol, any patient over the age of 17 who presents to GI clinic with GERD or related symptoms and is either 1) being initiated on PPI therapy or 2) continues to have symptoms despite PPI therapy will be considered eligible for the study.

Exclusion Criteria. This study will exclude patients who have had extensive esophageal or gastric surgery or any major chronic illness or condition that in the opinion of the gastroenterologist that would interfere with participation in the study.

Participant Recruitment Methods.

Prior to enrolling their patients, clinicians at participating GI clinics (investigators for this study) will be asked to complete surveys that assess their knowledge, attitudes, and beliefs as they relate to pharmacogenetics testing.

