### **(c) Approach**

#### **Preliminary Data in support of this proposal**

Patients with CYP2C19 genotype and PPI exposure in the EHR at UFHealth and Vanderbilt. At UFHealth and Vanderbilt, more than 16,000 patients to date have undergone CYP2C19 testing, with 10,185 being prescribed a PPI. Of these approximately 20% are PMs (1 or 2 LOF alleles), 41% are NMs, and 33% are RMs (1 or 2 GOF alleles), and approximately 7% with genotype combinations with unknown phenotypes. The goal of this analysis will be to evaluate the relationship with overall metabolism (poor vs normal vs rapid) with clinical outcomes. The hypothesis is that PMs will have increased rates of acid suppression and associated increased rates of bone fractures, infection, and chronic kidney disease and dementia while RMs are more likely to develop refractory GERD (inadequate acid suppression) and lower rates of PPI-related complications.

Lansoprazole pharmacokinetic data and CYP2C19 genotype. Table 2 demonstrates the relationship between plasma drug concentrations and CYP2C19 genotype.

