The study is also feasible for enrollment over 9 months, with 3 months follow-up based on volume of the clinics at UF and Nemours. Specifically, the three adult GI providers at UF Health who will be participating in this trial will enroll patients from 10 clinics/wk, which represents approximately 150 patients/wk. Of these, approximately 40% of patients are being seen for peptic acid/GERD indications which should produce 50-60 pts/week that meet inclusion criteria. Assuming only half of eligible patients consent to the study, we anticipate enrolling the 350 adults within a 12 week period. For 2014 and 2015 providers in the Division of Gastroenterology at the Nemours Children's Hospital saw 722 and 877 pediatric patients, respectively, who received a prescription for a PPI. For those years 1207 and 1525 respective prescriptions were written for a PPI. Currently the Division sees 20-30 pediatric patients/week that meet the inclusion criteria. Assuming we see 20 patients/week, we expect to enroll at least one-third to one-half of them, which would allow enrollment of 250 patients 6-9 months.

Recent data suggests that in a period of 6-9 months, approximately 60 patients will meet criteria and be enrolled in the study at Nemours Children's Hospital (NCH) alone. In a period of one month (June-July 2016), on average, 71% of PPI prescriptions were performed at GI Clinics from the Nemours Health System (i.e LKM, 1717 ORL, MELB, Lake Nona-NCH) and the remaining were prescribed in other clinics such as

LKM Otolaryngology Clinic and others. At NCH, on average, 38 % of the patients prescribed with a PPI therapy are prescribed at NCH GI Clinic alone. (**Table 4**)

Table 4. PPI prescriptions in a month at Nemours, Orlando

	Unique MRNs	PPI prescribed at GI Clinics	PPI prescribed at other clinics*	PPI prescribed at NCH GI Clinic
Week 1	33	24	9	10
Week 2	34	24	10	15
Week 3	25	16	9	10
Week 4	48	36	12	18

\*i.e. LKM Pulmonology, MLB Reumatology, NCH Nephrology, NCH Neurology, NCH orthopedics, NCH Otolaryngology, LKM Otolaryngology, NCH, Allergy/Inmunology, NCH, Plastic Surgery, 1717 ORL Genetics, NCH Nutrition, 1717 ORL Oncology, 1717 ORL Nephrology, 1717 ORL Otoralyngology, others

In order to improve enrollment efforts, Spartan RX genetic testing equipments will be required at Nemours satellite GI Clinics (i.e. LKM, MELB, 1717 ORL).

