Study Design. The study is a randomized, open-label, comparative effectiveness clinical trial in 180 patients (60 children, 120 adults) with GERD or any stomach acid mediated condition that will require a PPI. Patients will volunteer to be randomized to either conventional PPI treatment or genotype-supported PPI treatment. All participants will have symptoms of GERD or related diseases who are candidates for PPI therapy or who are on PPI therapy and classified as refractory GERD. Adult patients will be enrolled at UF Health Gastroenterology Clinics and children will be enrolled at the Nemours Children's Hospital Gastroenterology Clinics. After obtaining informed consent, participants will be genotyped and randomly assigned to either conventional treatment or genotype-supported PPI therapy using a randomization table. At NCH, study participants in the control/conventional arm will be blinded on CYP2C19 metabolizer status. Study staff members will not be blinded to any study procedures or determinations as this will improve and facilitate study feasibility. At the end of study period (i.e. 8-12 weeks) study participants in the control/conventional arm will be revealed of metabolizer phenotype status. We will also collect data from the health records for up to 24 months after enrollment on upper respiratory infection (cold), sore throat, strep throat, bronchitis, pneumonia, ear infection, acute sinusitis (sinus infection), bone fractures, renal function, and gastrointestinal infections for preliminary assessment of the effects of CYP2C19-supported PPI dosing on adverse effects.

Participation stipends. Each participant will receive \$25 dollars at the end of study participation. Participants must have completed all study procedures by the end of the study period in order to receive the complete study stipend. If a study participant decides to withdraw from study before the end of study period (before 3 months), the participant will receive a pro-rated stipend. A deposit will be provided in a single CT Payer master card. Each participant will be provided a CT Payer (master card) at the moment of consent. The CT Payer card will be uploaded with the stipend at the end of study participation. Participants whom insurance coverage is limited, a separate deposit will be provided to cover study therapy expenses. We expect to incur in study drug expenses for participants with higher PPI dose prescriptions than conventional dosing (i.e. RMs and UMs).

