Statistical analysis. We will have two primary hypotheses tested in this pragmatic clinical trial: 1. Hypothesis: RMs (1 or 2 GOF alleles) in the genotype-supported arm have better GERD control than RMs in the usual care group 2. Hypothesis: PMs (1 or 2 LOF alleles) in the genotype-supported group have fewer adverse effects (composite of URI/GI infections, kidney adverse effects, bone fracture) than PMs in the usual care group. Continuous variables will be compared between the genotype-supported group and the usual care group using t-test, and categorical variables will be compared using the chi-squared test. The hypotheses will be tested by logistic regression analysis to estimate the odds ratios and 95% confidence intervals for GERD control rate in the RM patients between the two arms and for the adverse events between the PM patients between the two arms. Time to-event analysis will be performed using Kaplan Meier method and a Cox regression model. Significant covariates associated with the events will be adjusted for in the multivariable models. All analysis will be performed in SAS 9.4 (Cary, NC).

We will also have a composite analysis that is conducted in the same manner that combines efficacy and safety and tests the hypothesis that genotype supported PPI dosing leads to better PPI efficacy and safety, as determined by composite of refractory GERD, and adverse effects.

Finally, we will evaluate the influence of genotype-supported dosing recommendations and will evaluate the percentage of the time when a dosing recommendation was made and accepted by the treating clinician, to provide practical data on the willingness of clinicians to adopt this approach. We will also collect patient- and provider-level survey data on attitudes about pharmacogenetics testing; using survey tools adapted from those utilized by other IGNITE groups. These will be shared for network-wide analyses, but because of the number of patients we will study, we should also have sufficient data to perform analyses on our patients along.

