Power calculation. Briefly, with 600 participants in the trial, we will have 80% power at alpha level of 0.05 to detect a relative risk of 1.35 or higher in the GERD control within RM patients in the usual care vs. the genotype-supported arm. This assumes that among the 600 participants, 33% will have the RM phenotype, and half will be randomized to each arm of the study. For the adverse event hypothesis, with 600 patients, we expect to have 178 PM patients, with 89 patients in each arm. At alpha level of 0.05, we will have 80% power to detect relative risk reduction of 29% or more in the adverse events for PM patients in the genotype supported group compared to those in the usual care group.

Clinical Trials.gov. This trial requires registration in ClinicalTrials.gov.

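### The Nemours power statement is worked out for 600 participants, but the trial enrols 180, so the stated 80% power for both primary hypotheses does not apply

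*Combined protocol and SAP*

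**What the plan says.** The Statistical analysis paragraph of the Nemours protocol announces the confirmatory structure: "We will have two primary hypotheses tested in this pragmatic clinical trial". The first is better GERD control in RMs (one or two gain-of-function alleles) under genotype-supported dosing than under usual care. The second is fewer adverse effects, as a composite, in PMs (one or two loss-of-function alleles). Both are to be tested by logistic regression.

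The Power calculation paragraph then says that "with 600 participants in the trial, we will have 80% power at alpha level of 0.05 to detect a relative risk of 1.35" or higher for the first hypothesis, with 33% of participants being RMs and half of them in each arm. For the second it says "we expect to have 178 PM patients, with 89 patients in each arm", and claims 80% power for a relative risk reduction of 29% or more.

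The number of patients is given differently elsewhere:

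- Nemours protocol, Study Design: "comparative effectiveness clinical trial in 180 patients (60 children, 120 adults").
- UF protocol, section 7 (Research Plan): "comparative effectiveness clinical trial in 180 total patients with GERD or dyspepsia symptoms".
- Nemours protocol, feasibility text, adults: "we anticipate enrolling the 350 adults within a 12 week period".
- Nemours protocol, feasibility text, children: "which would allow enrollment of 250 patients 6-9 months". The next paragraph expects about 60 at Nemours Children's Hospital.

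On genotype shares, the Nemours preliminary data say: "Of these approximately 20% are PMs (1 or 2 LOF alleles), 41% are NMs, and 33% are RMs (1 or 2 GOF alleles"). Table 1 gives 20% intermediate plus 1.7% poor metabolizers.

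**The concern.** The two feasibility targets add up to 350 + 250 = 600, the number used for power. The design text has moved to 120 + 60 = 180, but the power paragraph and part of the feasibility text have not. Both figures stand as current statements, so the text contradicts itself.

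Both hypotheses are tested within genotype subgroups, so the shortfall falls on groups that are already small. Someone who relies on the power paragraph would expect a good chance of detecting a relative risk of 1.35 or a 29% reduction. A non-significant result could then be taken as evidence against genotype-supported dosing when the comparison had little chance of showing a difference. Study Design does call the 24-month health-record data on adverse effects preliminary. However, the Overview of Aim 2 still makes an adverse-event composite the primary outcome, and the Statistical analysis paragraph still lists it among the primary hypotheses.

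**Working it through.** **Numbers per arm** (share × N / 2, 1:1 allocation)

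| | N = 600 | N = 180 |
|---|---|---|
| RMs at 33% (power paragraph) | 600 × 0.33 / 2 = 99 | 180 × 0.33 / 2 = 29.7 |
| PMs at 178/600 = 29.7% (power paragraph) | 178 / 2 = 89 | 180 × 0.297 / 2 = 26.7 |
| PMs at 20% + 1.7% = 21.7% (Table 1) | 600 × 0.217 / 2 = 65.1 | 180 × 0.217 / 2 = 19.5 |

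Below, 30 RMs and 20 to 27 PMs per arm are used for N = 180.

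**Can the plan's 80% be reproduced?** Not from stated inputs. The power paragraph gives no usual-care rate for GERD control or for adverse events, and does not say whether the test is one- or two-sided. Two-sided 0.05 is assumed here.

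**Step 1: change only the sample size, with no event rate assumed.** Accept 80% at 600. With effect and rates held fixed, power is approximately Φ[(1.960 + 0.842) × √(n new / n old) − 1.960].

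- N alone, both hypotheses: ratio 180/600 = 0.30, so 2.802 × 0.548 − 1.960 = −0.425, and power is about 34%.
- PMs with Table 1's share as well: ratio 20/89 = 0.225, so 2.802 × 0.474 − 1.960 = −0.632, and power is about 26%. This changes two things, N and the PM share.

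**Step 2: two-proportion calculation** (normal approximation, pooled variance under the null). With p̄ = (p₁ + p₂)/2, power = Φ{[|p₁ − p₂| − 1.960 √(2p̄(1 − p̄)/n)] / √[(p₁(1 − p₁) + p₂(1 − p₂))/n]}.

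The usual-care rates that give exactly 80% at 600 were solved for, and then n was changed.

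| | Usual care → genotype arm | N = 600 | N = 180 | Effect detectable with 80% power at N = 180 |
|---|---|---|---|---|
| RM, RR 1.35 | 54.3% → 73.4% | 80% (99 per arm) | 33% (30 per arm) | RR about 1.60 |
| PM, 29% reduction | 70.4% → 50.0% | 80% (89 per arm) | 26% to 33% (20 to 27 per arm) | 61% to 53% reduction |

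**Step 3: other usual-care rates** (all assumed)

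- RM, RR 1.35, 30 per arm: control rates of 40, 50, 60, 65 and 70% give power of 19, 28, 43, 55 and 71%.
- PM, 29% reduction, 20 per arm: event rates of 30, 50, 70 and 90% give about 9, 15, 25 and 50%. With 27 per arm they give about 11, 19, 33 and 63%.

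None of these reaches 80%. For RMs, a one-sided test that has 80% power at 600 gives 39% at 180. A continuity-corrected test gives 26%.

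**The 178 PMs.** This count is 29.7% of 600. Table 1 implies 600 × 0.217 = 130, and the preliminary-data share implies 600 × 0.20 = 120. The nearest figure in the documents is the share of *2 carriers among control children in Table 4 of the UF preliminary data: (75 + 4)/278 = 28.4%, or about 170 of 600. That does not match exactly and may include *2/*17. With 60 to 65 PMs per arm and the back-solved event rate, power is about 63% to 67% even with 600 patients.

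**The 60 children alone.** There would be about 10 RMs and 6.5 to 9 PMs per arm. Step 1's formula at ratio 60/600 gives about 14%. At such counts the approximation is rough: Fisher's exact test at the back-solved rates gives about 5% for 10 RMs per arm and about 7% for 9 PMs per arm.

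**The case against.** The strongest reply is that the 180-patient trial does have a power basis. The power section of the UF protocol gives 80% power for an RDQ effect size of 0.74 with about 30 RMs/UMs per arm, and this reproduces (80.5% by the t-test). So symptom control in rapid metabolizers is not without support at 180. But that is a continuous score difference. It does not carry over to a binary control rate at a relative risk of 1.35, and it says nothing about PMs or adverse events. The other UF calculations at 180 compare *17 carriers with non-carriers on pH-probe measures, which is a different contrast.

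Three further points stand, without altering the conclusion:

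- The size of the loss depends on usual-care rates that the plan does not give. The Nemours Significance section says treatment fails in up to 40%, which suggests control of about 60% or more overall. RM power at 180 could then be 43% at 60% control, or as high as 71% at 70%. At those same rates, 600 patients would give about 91% and over 99%, so they are not the rates behind the stated 80%.
- The available text describes one joint trial of 180 and specifies no children-only test, so the figures for the 60 children matter only if they are analysed alone.
- No definition of binary GERD control was found, and the two sites use different questionnaires. A restated power figure has to be tied to such a definition.

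One part of the Nemours Aim 2 text, just before the feasibility paragraph, was not in the copy reviewed. It could not make 600 agree with 180.

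**Conclusion.** The concern holds. The mismatch between 600 and 180 is explicit in the current text and needs no assumption. No available section gives power at 180 for either Nemours primary hypothesis.

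On the plan's own terms, power falls from 80% to about 34% for each hypothesis, or to about 26% for PMs with Table 1's share. These figures assume a two-sided 0.05 test and that the 80% at 600 was correct. The detectable effects of about RR 1.60 and a 53% to 61% reduction also depend on the back-solved rates of 54.3% and 70.4%. The exact values move with the usual-care rates, but stay below 80% throughout the ranges tried. The count of 178 PMs is a further unsupported input, since it exceeds what the plan's own genotype frequencies imply. This must be corrected, because the stated power concerns both hypotheses declared primary.

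**What to change.** Rewrite the Power calculation paragraph of the Nemours protocol for 180 patients, and add a statement for the 60 children if they will be analysed alone. It should give:

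- the assumed usual-care rates of GERD control and of the adverse-event composite, with their sources;
- the RM and PM shares with their sources, explaining or replacing the 178, and saying how *2/*17 is counted;
- the resulting numbers per arm, and whether the test is one- or two-sided;
- the resulting power at the effects of interest, or the effect detectable with 80% power.

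Reconcile the targets of 350 adults and 250 children in the feasibility text with the 120 and 60 in Study Design.

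The cost is editorial: one paragraph rewritten and two targets corrected. The two hypotheses can stay and no extra patients are needed. The stated power will be much less favourable, and the paragraph should say so openly.

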### **Analysis Plan and Power Calculations:**

We will test the hypothesis that RMs/UMs (1 or 2 gain-of-function alleles) in the genotype-supported arm have better GERD and symptom control than RMs/UMs in the conventional treatment group because they will have their dose increased based on their genotype.

Continuous variables will be compared between the genotype-supported group and the conventional treatment group using the Student's unpaired *t*-test, and categorical variables will be compared using the chi-square or Fisher's exact test. The hypotheses will be tested using linear regression analysis to estimate the difference in the RDQ reduction in the RM/UM patients between the two arms. All analysis will be performed in SAS 9.4 (Cary, NC).

We will evaluate the percentage of the time when a dosing recommendation was made and accepted by the treating clinician, to provide practical data on the willingness of clinicians to adopt this approach. We will also collect patient- and provider-level survey data on knowledge, attitudes, and beliefs about pharmacogenetics testing, using survey tools adapted from other IRB-approved studies.

Power calculation. While there are no data in the literature on genotype associations with the efficacy endpoint we will use (symptom improvement), there are pH probe data by genotype that were generated by the Nemours investigators, that we can use, and this should be an excellent surrogate for symptom data. We have done power calculations based on two of the pH-based response phenotypes, found in Table 3. Specifically we powered based on percent time with pH < 4 (which has an effect size of 0.79) and acid clearance time (effect size of

0.45). Based on these two phenotypes, we have the following power to detect differences in efficacy between *CYP2C19\*17* carriers and non-carriers:

Based on the previous data for acid clearance time, with 180 total participants (120 from UF Health and 60 from Nemours), we have 81% power to detect a 0.49 effect size.

Based on the previous data for time with pH <4.0, with 180 participants, we have >99% power to detect a 0.79 effect size.

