## **SPECIFIC AIMS**

Proton Pump Inhibitors (PPIs) are indicated for the treatment of gastroesophageal reflux disease (GERD), H.pylori infection, peptic ulcer disease, and gastric protection in patients at risk for gastrointestinal bleeding. PPIs are among the most commonly prescribed drugs in the world and their most common indication is GERD.

Refractory GERD is the term used to describe non-responsiveness to conventional PPI therapy, and it occurs in up to 40% of patients (both children and adults) even when the PPI dose is doubled. The efficacy of PPIs is highly dependent on plasma concentrations achieved following drug administration. All PPIs are metabolized in part by the CYP2C19 enzyme located in the liver, which is encoded by the highly polymorphic CYP2C19 gene.

Depending on the CYP2C19 genotype, individuals are classified into different metabolizer phenotypes: poor metabolizers (PM, 2 loss-of-function CYP2C19 alleles); intermediate metabolizers (IM, one loss-of-function allele); normal metabolizers (NM, no loss or gain-of-function alleles); rapid metabolizer (RM; one gain-of-function allele) and ultra-rapid metabolizers (UM, two gain-of-function alleles). Genetic variants in CYP2C19 are known to profoundly influence PPI plasma concentrations and therefore, response to PPI therapy. For example, individuals classified as either RM or UM have lower PPI concentrations compared to NM or of loss-of-function (LOF) allele carriers, respond poorly to PPI therapy and some fail to respond even when the PPI dose is doubled.

Short- and long-term use of PPIs has been associated with a number of significant adverse effects, which may be influenced by CYP2C19 genotype. Examples of serious adverse effects associated with PPIs included: 1) vitamin/mineral malabsorption associated with increased risk of bone fractures (calcium deficiency); 2) increased risk of intestinal infections (*Clostridium difficile* and small bowel bacterial overgrowth) and pulmonary infections (community and hospital-acquired), and 3) acute interstitial nephritis, chronic kidney disease and end stage renal disease; Some of these adverse effects have been linked to increasing gastric acid suppression or higher than conventional PPI doses. In a recent study reported by Dr.[name], children taking lansoprazole to treat poorly controlled asthma had a higher risk of infection compared to placebo, and the increased risk of infection was observed in IMs and PMs but not in NM, RM or UM patients.

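### The 80% power stated for GERD control in rapid metabolizers is computed on 600 participants with no control rate given; at the planned 180, the scenario behind it has about 33% power

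*Combined protocol and SAP*

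**What the plan says.** The Nemours protocol names two primary hypotheses. The first is that RMs, defined there as carriers of one or two gain-of-function alleles, have better GERD control under genotype-supported dosing than under usual care. The analysis is binary: "The hypotheses will be tested by logistic regression analysis to estimate the odds ratios and 95% confidence intervals for GERD control rate".

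Its Power calculation paragraph states "80% power at alpha level of 0.05 to detect a relative risk of 1.35 or higher in the GERD control", the comparison being "within RM patients in the usual care vs. the genotype-supported arm". The assumptions listed are "with 600 participants in the trial" and that "33% will have the RM phenotype, and half will be randomized to each arm of the study". It gives no GERD control rate for either arm, no sidedness and no allowance for dropout.

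The Study Design paragraph of the same protocol plans 180 patients, 60 children and 120 adults. The UF Health protocol gives the same total and, under Analysis Plan and Power Calculations, expects about 30 RM/UM patients per arm.

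The only failure figures concern all patients. The Nemours Abstract puts PPI failure at 40%, and Significance at up to 40%. Specific Aims says of refractory GERD that "it occurs in up to 40% of patients (both children and adults) even when the PPI dose is doubled". RMs and UMs are described only in words, as patients who "respond poorly to PPI therapy and some fail to respond even when the PPI dose is doubled".

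**The concern.** With a binary outcome, a relative risk and a sample size do not determine power; the control-arm rate is also needed. The paragraph omits it, so a reader cannot reproduce the 80% or judge whether the implied rates are plausible. The sample size is also not the one the protocol plans: the subgroup being tested is less than a third of the size assumed.

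This matters because the figure supports one of two primary hypotheses. If 80% is taken at face value and the comparison is null, the result could be read as evidence that genotype-supported dosing does not help RMs, when the trial had little chance of detecting the effect it was said to be powered for.

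**Working it through.** **Inputs.** Relative risk 1.35, alpha 0.05, 600 participants, 33% RM, 1:1 allocation (Nemours, Power calculation). Planned total 180 (Nemours, Study Design). About 30 RM/UM per arm (UF Health, Analysis Plan and Power Calculations). My assumptions: two-sided test, no dropout, no covariate adjustment.

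**RMs per arm.** As assumed: 600 × 0.33 / 2 = 99. As planned: 180 × 0.33 / 2 = 29.7, which agrees with the UF Health figure of about 30.

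**Formula.** Two-proportion z-test with pooled null variance. With p1 the usual-care rate, p2 = 1.35 × p1 and m = (p1 + p2)/2:

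power = Φ{ [ (p2 − p1)√n − 1.96 √(2m(1 − m)) ] / √( p1(1 − p1) + p2(1 − p2) ) }

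**Reproducing the stated 80%.** This is not possible from the stated inputs, because p1 is missing. Solving for p1 at n = 99 gives p1 = 0.5434 and p2 = 0.7335. Check: 0.1902 × 9.950 = 1.892; 1.96 × 0.6795 = 1.332; (1.892 − 1.332)/0.6660 = 0.84; Φ(0.84) = 0.80. The answer moves little with the method: 55.0% on a Wald log odds ratio, 55.5% on a Wald log relative risk, about 56.5% with continuity correction. A one-sided test needs 49.5%.

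**The same rates at n = 30.** 0.1902 × 5.477 = 1.042; (1.042 − 1.332)/0.6660 = −0.44; Φ(−0.44) = 0.33.

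**Power at a relative risk of 1.35 over a range of control rates.**

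| Usual care | Genotype-supported | 99 per arm | 30 per arm |
|---|---|---|---|
| 30% | 40.5% | 34% | 13% |
| 40% | 54% | 50.5% | 19% |
| 44.4% | 60% | 59% | 22% |
| 50% | 67.5% | 71% | 28% |
| 54.3% | 73.4% | 80% | 33% |
| 60% | 81% | 91% | 43% |
| 72.3% | 97.7% | over 99% | 80% |

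**Where the 40% failure figure leads at 99 per arm.** It implies 60% control, but the documents do not say which arm or subgroup that describes.

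- Genotype-supported arm at 60%: usual care is 60/1.35 = 44.4%, power 59%.
- Usual care at 60%: the other arm is 81%, power 91%.
- Ratio read on failures, usual care at 40%: 40% versus 29.6%, power 33%.
- Ratio read on failures, genotype-supported arm at 40%: 54% versus 40%, power 50.5%.

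The failure readings need considering because the paragraph orders the ratio as usual care over genotype-supported. A value above 1 in that order fits failure better than control.

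**Detectable relative risk at 80% power.** At usual-care control of 30%, 40%, 50% and 60%, the same formula solved for p2/p1 gives 1.65, 1.50, 1.39 and 1.31 with 99 per arm. With 30 per arm it gives 2.18, 1.88, 1.67 and 1.51.

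**The case against.** A reader might infer something stronger: that the 80% holds only if control rises from 54% to 73%, that the plan's own failure figures rule this out, and that power at 600 is therefore 59% or less. The documents do not support that.

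- Any usual-care rate of about 54% or higher gives at least 80% at 99 per arm, so the pair is a threshold, not a single condition.
- No RM-specific rate is given. Usual-care control of 54% in RMs fits 40% failure overall: with 33% RMs at 54% and the rest at 63%, the average is 0.33 × 54 + 0.67 × 63 = 60%.
- The 59% depends on placing the 40% in the genotype-supported arm, on the strength of the doubled-dose sentence. The other statements of 40% mention no raised dose, and placing it in usual care gives 91%.
- An upper limit of 40% on failure makes 60% a lower limit on control for all patients. On that reading 59% is a minimum, unless RMs do worse by an amount the documents do not give.
- The 73% target sits uneasily with the doubled-dose sentence, but the plan's premise is that RMs are underexposed, so an all-patient figure does not cap their response.

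These points stand, and they leave an unreported input rather than a demonstrated arithmetic error at 600. Asking only for the rate to be written down would be a minor request.

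It could also be said that 600 is not an isolated figure, since the Nemours feasibility text still speaks of 350 adults and 250 children. That text goes on to expect about 60 patients at Nemours, and the Study Design paragraphs of both protocols say 180. The UF Health protocol does give a power statement for about 30 per arm, but for a standardized difference in RDQ score. It does not carry over to the Nemours binary hypothesis.

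**Conclusion.** The stated 80% does not describe the planned trial. The rates that would give it at 600 participants (about 54% versus 73%) give about 33% at 180. Across the scenarios 44% versus 60%, 54% versus 73% and 60% versus 81%, power is about 22%, 33% and 43%. Reaching 80% at 30 per arm needs usual-care control above about 72% (about 70% one-sided), with nearly every RM in the other arm controlled: 72.3 × 1.35 = 97.7%.

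At 600 the figure cannot be verified. Depending on which arm the 40% describes and which way the ratio runs, power lies anywhere from 33% to 91%. It would be wrong to conclude that it is below 80% there.

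These results assume a two-sided 5% test, no dropout and 33% RMs split evenly. At 30 per arm the normal approximation is rough, so the percentages are indicative. The gap from 80% is far larger than that uncertainty over any usual-care rate up to 60%.

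**What to change.** In the Nemours Power calculation paragraph, replace the 80% statement with the power, or the detectable relative risk, computed on the RMs expected among 180 patients (about 30 per arm). Give the assumed usual-care and genotype-supported control rates as two percentages with their difference, over a stated range such as 30% to 60% under usual care. State whether the ratio is of control or of failure, which arm is the numerator, and whether the test is one- or two-sided.

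This changes protocol wording only and adds no enrolment. The cost is a less favourable stated power: over that range, about 13% to 43% at a relative risk of 1.35, or a detectable relative risk of about 2.18 down to 1.51.
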